19.7 Exploratory endpoint analysis

Red blood cell membrane EPA content will be measured at baseline, at surgery and 6 months after surgery in all participants from Leeds and Sheffield⁵². The effect of red blood cell membrane EPA content on disease-related outcomes (PFS and OS) will be analysed using an extended Cox model (if appropriate) which will adjust for the minimisation factors and regular aspirin use during follow-up, which will be included as a time dependent covariate and will also include red blood cell membrane EPA content as a time dependent covariate. Subsequent sensitivity analyses will be conducted to adjust for any other potential effect modifiers in addition to the minimisation factors.

Lean body mass will be measured longitudinally from the routine CT abdomen images using the method of Baracos (based on muscle area at the L3 vertebral level)⁴⁴. The difference in muscle mass between the EPA and placebo treatment groups will be analysed using a random effects (multi-level) model to account for the hierarchical nature of the repeated measures data. The model will be adjusted for the baseline muscle mass, minimisation factors and

regular aspirin use during follow-up, which will be included as a time dependent covariate, with a subsequent sensitivity analysis to adjust for any other potential effect modifiers in addition to the minimisation factors. A possible association between changes in muscle mass and disease related outcomes (PFS and OS) will be analysed using an extended Cox model (if appropriate) which will adjust for the minimisation factors and regular aspirin use during follow-up, which will be included as a time dependent covariate, and will also include lean body mass as a time dependent covariate. A subsequent sensitivity analysis will be carried out to adjust for any other potential effect modifiers as well as the minimisation factors.

Weight will also be analysed as a measure of cachexia. The difference in weight of patients between the treatment arms will be analysed using a random effects (multi-level) model to account for the hierarchical nature of the repeated measures data and will be adjusted for baseline weight, the minimisation factors and regular aspirin use during follow-up, which will be included as a time dependent covariate. A sensitivity analysis will also be carried out to adjust for other potential effect modifiers as well as the minimisation factors.

Analysis of the biospecimens collected during the sub-study 'The prebiotic effect of EPA treatment for CRCLM' are detailed in Appendix A of the Biospecimen Collection protocol. Laboratory work will take place in Leeds Institute of Medical Research and ICT, University of Bradford, as well as Massachusetts General Hospital and Harvard School of Public Health in Boston, USA.

20. Trial Monitoring

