Pancreatic lipase stimulated by food (especially fat) intake hydrolyses O3FA-TGs producing O3FA FFAs, which are absorbed by small intestinal enterocytes before re-esterification to the TG form for chylomicron transport to the liver and eventual systemic distribution leading to incorporation into all plasma cell membranes⁹. Omega-3 fatty acid EEs require hydrolysis by carboxyl-ester lipase (also known as bile salt-dependent lipase) in order to generate FFAs for enterocyte uptake⁹. Presence of pancreatic lipase and carboxyl-ester lipase in the intestinal lumen is critically dependent on stimulation of pancreatic secretion by food intake. Food fat content has been demonstrated to affect O3FA tissue incorporation after short-term administration of EEs¹⁰.

Systemic O3FA bioavailability is most accurately and reliably measured in clinical studies by quantification of red blood cell (RBC) O3FA levels¹¹. Oral dosing studies have determined that O3FA tissue incorporation approaches steady-state levels at two weeks after starting supplements, reaching a peak between 4-6 weeks, and that 'washout' to basal levels can take as long as 3 months¹². Recently, whole blood O3FA testing from dried finger-prick blood samples has emerged as an alternative to venepuncture needed for RBC isolation¹³. Preliminary data suggest a strong correlation between whole blood and RBC O3FA levels after O3FA supplementation¹³.

There have been few direct comparisons of bioavailability of EPA given as the FFA, TG and EE. Most studies have been short-term (≤ 2 weeks) and measured plasma/serum TG levels, which are of uncertain relevance to tissue omega-3 fatty acid incorporation⁹. In the studies of El Boustani *et al.*¹⁴⁻²⁰ and Lawson and Hughes^{1547, 1649}, plasma TG levels were higher after FFA administration than TG ingestion, when omega-3 PUFAs were given with a low-fat meal. Interestingly, in the longer study of Dyerberg *et al.*¹⁷, plasma TG levels after TG administration were in slight excess of those after FFA ingestion.

One comparison of tissue (RBC) EPA incorporation after longer-term mixed omega-3 PUFA administration as the -TG, -EE or krill oil (4 weeks) reported no significant difference between formulations with equivalent EPA and DHA content^{18ref}. In another long-term (6 months) comparison of mixed EPA/DHA administration in TG and EE forms in hyperlipidaemic subjects, TG treatment resulted in a significantly greater % RBC content of EPA than the EE group¹⁹.

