7.4 Exploratory Objectives

- To determine whether baseline, pre-operative and/or 6 month post-operative red blood cell EPA content predicts disease-related outcomes.
- To determine whether IPE treatment maintains muscle mass in CRCLM patients and whether there is any association between changes in muscle mass and disease related outcomes.

8. Design

The EMT2 study is a prospective randomised, double-blind, placebo-controlled, multi-centre, parallel-group, superiority phase III trial of the omega-3 fatty acid (O3FA) eicosapentaenoic acid (EPA) in patients undergoing liver resection surgery with curative intent for colorectal cancer liver metastases (CRCLM).

Eligible participants will be randomised on an equal basis to receive 4 x 1 g capsules per day of either icosapent ethyl (IPE; equivalent to 4 g of EPA-EE or 3656 mg EPA-FFA) taken as 2 capsules twice daily with food or 4 placebo (containing light mineral oil instead of IPE) capsules taken in an identical fashion.

The trial is designed to investigate whether EPA (IPE) treatment will result in an improvement in PFS (see section 17.1 for definition).

EMT2 is a double-blind trial design in which participants and site personnel will be blinded to the treatment allocation to minimise the possible introduction of bias.

All participants will be followed up for a minimum of 2 years until the last participant recruited reaches 2 years post liver resection (Please refer to Section 13 on Assessments/samples/data collection for more details on the follow-up schedule).

There is also the option for EMT2 participants to join a sub-study funded by The US National Institutes of Health called Prebiotic effect of eicosapentaenoic acid treatment for colorectal cancer liver metastases, in which biospecimens (stool, urine, blood, and tumour tissue) will be collected before and after EPA or placebo treatment (refer to the Biospecimen Collection protocol).

9. Eligibility

Eligibility waivers to inclusion and exclusion criteria are not permitted.

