13.4 Visit 2: CRCLM surgery, Treatment Assessments and Data Collection

Participants will have a trial visit during admission on the first day of the hospital inpatient stay for CRCLM surgery. The CRCLM surgery should be <6 weeks from post randomisation.

The following assessments will be carried out:

- Toxicity assessment: collection of any adverse events which may have occurred since the last research nurse telephone call.
- Details of hospital resource activity (e.g. hospital inpatient stays, outpatient clinics attending, accident and emergency attendances).
- Participant self-reported assessments: a health economics questionnaire will be administered to the participant in a Participant Questionnaire Visit 2 Pack. It is preferable that this is administered to the participant before surgery but if this is not possible within the timeframe pre-surgery, the Visit 2 Pack may be completed during the inpatient stay.
- Participants should be provided with a Participant Diary Booklet to record information over the next visit period. The information collected in the booklet will be the information to be collected in the health economics questionnaire and details on compliance and adverse events. The booklet is intended to act as a reminder to the participant and must not be handed in to clinic or returned to the CTRU.
- Weight in kilograms (in light indoor clothing and without shoes). This may be taken from the pre-operative assessment in the clinical records.
- Blood sample for red blood cell fatty acid analysis (for Sheffield Teaching Hospitals NHS Foundation Trust and Leeds Teaching Hospitals NHS Trust only). **Please note that it is preferable that the blood sample is obtained prior to surgery, ideally on admission to hospital.** A blood sample should be collected in two EDTA-coated Vacuette® tubes and agitated immediately to prevent clotting. The blood components should be separated within 30 minutes of taking the blood sample (see Section 13.16). If not processed immediately, store the two tubes in the fridge at 4°C for up to 30 minutes.
- See Biospecimen Collection protocol if participant is in this sub-study.
- Treatment compliance: the participant will be asked if they have missed any treatment doses since the last research nurse telephone call and for what reason.

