13.5 Visit 3: Treatment Assessments and Data Collection

Participants will have a trial visit 6 months +/- 2 weeks after the date of CRCLM surgery. For those participants having adjuvant chemotherapy the CT scan may be during the chemotherapy treatment period to ensure that the trial visit at 6 months +/- 2 weeks can be adhered to. For all participants the following assessments will be carried out:

- Clinical evaluation to assess for disease progression and new primary cancer, as per local standard practice.
- Toxicity assessment: collection of any adverse events which may have occurred since the last trial visit.
- Details of hospital resource activity (e.g. hospital inpatient stays, outpatient clinics attending, accident and emergency attendances).
- Participant self-reported assessments: the EQ-5D, EORTC QLQ-C30 and QLQ-LMC21 Quality of Life questionnaires and a health economics questionnaire will be administered to the participant in a Participant Questionnaire Visit 3-10 Pack. Questionnaires should be completed by participants at the time of clinical assessment, but before discussion of the outcome of any medical assessments or blood tests wherever possible.
- Participants should be provided with a Participant Diary Booklet to record information over the next visit period. The information collected in the booklet will be the information to be collected in the health economics questionnaire and details on compliance and adverse events. The booklet is intended to act as a reminder to the participant and must not be handed in to clinic or returned to the CTRU.
- Weight in kilograms (in light indoor clothing and without shoes).
- CT scan of thorax, abdomen and pelvis.
- Treatment compliance: the participant will be asked if they have missed any treatment doses since the last trial visit and for what reason.
- Details of concomitant medications including over-the-counter O3FA supplements since the last trial visit. Participants should be reminded that over-the-counter O3FA supplements are prohibited.

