- Blood sample for red blood cell fatty acid analysis (for Sheffield Teaching Hospitals NHS Foundation Trust and Leeds Teaching Hospitals NHS Trust only). A blood sample should be collected in two EDTA-coated Vacuette® tubes and agitated immediately to prevent clotting. The blood components should be separated within 30 minutes of taking the blood sample (see Section 13.16). If not processed immediately, store the two tubes in the fridge at 4°C for up to 30 minutes.
- See Biospecimen Collection protocol if participant is already in this sub-study.
- If the EMT2 participant has not already taken part in the Biospecimen Collection, an invitation to join the Biospecimen Collection sub-study to provide a single stool and urine sample should be extended to the participant using the dedicated post-surgery PIS/ICF (see Biospecimen Collection protocol).
- If new written informed consent for the Biospecimen Collection sub-study is obtained, a sample collection pack should be provided according to the Biospecimen Collection protocol.
- One box of IMP will be dispensed.
- The IMP dispensed at visit 2 should be checked regarding the expiry date and the participant should be advised to use the IMP box currently in use before opening the IMP box dispensed at visit 3.

For Visit 3 and all subsequent trial visits, follow-up can be on a remote basis by telephone interview, QoL questionnaires posted and courier delivery of IMP, if participants are unable to attend the recruiting hospital for repeat visits. Clinical evaluation, toxicity assessment, compliance and concomitant medication assessment, as well as determination of hospital resource activity, will be performed by telephone. Self-reported weight will be obtained. IMP will be delivered to the participant's postal address (see Section 11.3). CT scanning will be performed by the local Oncology team as per usual surveillance guidelines. Participants randomised in Leeds and Sheffield, but undergoing remote follow-up, will not be expected to provide blood samples for Visit 3.

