13.16 Red Blood Cell Fatty Acid Analysis

Blood samples taken at visits 1, 2 and 3 will be collected from participants recruited at two of the participating centres: Sheffield Teaching Hospitals NHS Foundation Trust and Leeds Teaching Hospitals NHS Trust. These samples will be analysed to measure the red blood cell fatty acid content which determines the absolute and relative content of the major O3FAs including EPA, as well as the EPA/AA and EPA+DHA/AA ratio⁵².

The fatty acid analysis on the baseline samples (see Section 13.2) will enable the investigation of whether O3FA status predicts subsequent therapeutic response to IPE. The absolute and differential O3FA levels at visits 2 and 3 will also act as a marker of compliance to IPE and allows the assessment of whether the placebo arm has been 'contaminated' by possible participant supplementation with over-the-counter O3FA.

At visits 1-3, whole blood will be collected in EDTA tubes for centrifugation and isolation of plasma and red blood cells. Both fractions will be stored locally at -30°C before courier transport of the complete sample sets to the Institute of Cancer Therapeutics (ICT), University of Bradford which will act as the central biobank. Lipid extraction from red blood cells followed by derivatisation and liquid chromatography-tandem mass spectrometry (LC-MS/MS) measurement of individual fatty acid (FA) species will be performed as described in the EMT2 Lab Manual⁵².

The red blood cell fatty acid analysis will be carried out centrally at the Institute of Cancer Therapeutics (ICT), University of Bradford.

The fatty acid analysis will be carried out on blood samples from all participants recruited at Sheffield Teaching Hospitals NHS Foundation Trust and Leeds Teaching Hospitals NHS Trust only.

At visits 1-3, whole blood will be collected for centrifugation and isolation of plasma and red blood cells. Blood samples will be obtained using the BD Vacutainer® system, following local Trust practice. Two purple cap K₂EDTA 6ml tubes will be filled to capacity. Tubes should be agitated immediately to prevent clotting.

The blood components should be separated within 30 minutes of taking the blood sample. If not processed immediately, the two K₂EDTA Vacutainer tubes should be stored in the fridge at 4°C for up to 30 minutes.

Separation of blood components will be achieved by centrifugation of the sample in K₂EDTA Vacutainers in a centrifuge, preferably refrigerated.

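### A single time-dependent EPA covariate (Protocol 19.7) pools three measurements into one coefficient, so the exploratory question about baseline EPA is effectively untested

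*Protocol*

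**What the plan says.** The exploratory objective in Protocol section 7.4 is "To determine whether baseline, pre-operative and/or 6 month post-operative red blood cell EPA content predicts disease-related outcomes". Section 13.16 gives the baseline sample a further purpose, to see whether omega-3 status predicts the response to IPE.

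Sampling is limited: "Blood samples taken at visits 1, 2 and 3 will be collected from participants recruited at two of the participating centres". Visit 1 is baseline and visit 2 is the surgical admission, for which section 13.4 says "The CRCLM surgery should be <6 weeks from post randomisation". Visit 3 follows under section 13.5: "Participants will have a trial visit 6 months +/- 2 weeks after the date of CRCLM surgery". Leeds and Sheffield participants followed remotely "will not be expected to provide blood samples for Visit 3".

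Section 19.7 then describes how EPA content is to be related to the two survival outcomes. Its effect "will be analysed using an extended Cox model (if appropriate) which will adjust for the minimisation factors and regular aspirin use during follow-up"; in addition, the model "will also include red blood cell membrane EPA content as a time dependent covariate". The only further analyses named add other potential effect modifiers. No model with baseline EPA as a fixed covariate, no landmark model and no EPA-by-treatment term is mentioned.

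**The concern.** A time-dependent covariate relates the hazard at each event time to the value in force at that moment. With one such covariate there is one coefficient, averaged over whichever value applied when events occurred. It answers whether current EPA is associated with current hazard. It does not answer whether a measurement taken on a named date predicts what happens afterwards, which is what section 7.4 asks.

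The baseline value suffers most. It is replaced at surgery a few weeks later, so a lasting association with pre-treatment EPA could be reported as null simply because the model hardly uses that value. The response-to-IPE question in section 13.16 needs an interaction with treatment arm, and the named model has none. At stake is whether the blood collected at two centres can answer the question it is collected for.

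**Working it through.** **Anchor.** Section 18.1.1 gives HR 0.7, 80% power, two-sided 5% and 247 events. Schoenfeld: 4 × (1.960 + 0.842)² / (ln 0.7)² = 246.8, so 247 is reproduced.

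**Event model.** PFS is taken as exponential with the protocol's medians of 21 and 30 months: λ = ln 2 / 21 = 0.0330 and ln 2 / 30 = 0.0231 per month. Accrual is uniform (24 months originally, 67 revised) with 24 months' minimum follow-up. The event probability averaged over arms is 0.6232 (24 months) or 0.7628 (67 months). Allowing for dropout, 247 / 0.6232 / 0.90 gives 441 participants (protocol 448) and 247 / 0.7628 / 0.85 gives 381 (protocol 388). Both are within 3%, so the model is a fair stand-in for the protocol's own.

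**Value in force at the event.** Assume current-value coding. The baseline value applies from 0 to s, the pre-operative value from s to s + 6, and the visit 3 value after that, where s is months from randomisation to surgery. I take s = 0.5 (2 weeks) to s = 1.38 (6 weeks). The share for an interval (a, b] is the arm average of exp(−λa) − exp(−λb), with a and b truncated at the censoring time, divided by the event probability.

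Worked case, 67 months' accrual and s = 1.38:
- Baseline: (0.0445 + 0.0314) / 2 = 0.0380; 0.0380 / 0.7628 = 5.0%
- Pre-operative: (0.1717 + 0.1254) / 2 = 0.1486; 0.1486 / 0.7628 = 19.5%
- Visit 3: the remaining 75.5%

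| Accrual | s (months) | Baseline | Pre-operative | Visit 3 |
|---|---|---|---|---|
| 24 | 0.5 | 2.2% | 24.5% | 73.3% |
| 24 | 1.38 | 6.1% | 23.8% | 70.1% |
| 67 | 0.5 | 1.8% | 20.0% | 78.2% |
| 67 | 1.38 | 5.0% | 19.5% | 75.5% |

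These shares pool both arms. In the IPE arm alone, with 67 months' accrual, the pre-operative share is about 18%.

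**In numbers.** The protocol gives no size for the EPA set. Section 18.1.1 uses 128 participants (64 per arm) for the muscle analysis at the same two centres, and I borrow that as an assumption. PFS events before surgery: 64 × (0.0164 + 0.0115) = 1.8 for s = 0.5, and 64 × (0.0445 + 0.0314) = 4.9 for s = 1.38. This is an upper figure, since the first routine post-operative CT is at visit 3. Deaths alone, with 2-year OS of 80% and 90%, would be about 0.4 to 1.2.

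**Consequence (illustrative simulation).** The setting was n = 128, surgery at 1 month, median PFS 21 months, and treatment arm in the model. Only baseline EPA acted on the hazard (HR 1.4 per SD, log-HR 0.336). There were 150 runs per row, so the power figures carry a simulation error of up to about 0.04.

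| Within-arm correlation of later EPA with baseline | Fixed baseline covariate: mean log-HR, power | Single time-dependent covariate: mean log-HR, power |
|---|---|---|
| 0 | 0.36, 0.92 | 0.00, 0.03 |
| 0.3 | 0.35, 0.89 | 0.09, 0.16 |
| 0.6 | 0.35, 0.94 | 0.17, 0.39 |

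The effect size and correlations are assumptions. The table shows direction, not expected power.

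**The case against.** **The SAP could settle this.** Section 19.1 promises a full SAP, section 19.7 hedges with an if-appropriate clause, and the coding of a time-dependent covariate is ordinary SAP content. That holds for the coding: the protocol does not say how EPA is valued between or after samples, so current-value coding is my assumption. It does not remove the mismatch. The protocol fixes a model form, names no alternative, and that form yields one pooled coefficient under any coding of a single current value.

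**The objective says and/or.** It does not strictly promise three separate answers, and a repeated-measures model is a recognised approach to such wording. Fair, but baseline is named in section 7.4 and given its own purpose in section 13.16, and the model leaves it almost unused.

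**The 6-week limit is a target.** If surgery is late or cancelled, or the visit 2 sample is missing, the baseline value stays in force longer. This widens the range but does not change the picture for a trial run as planned.

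A reader might also infer two stronger points, and the documents support neither:
- *That the visit 3 value is carried for years past washout.* Section 6.2 says the fall "to basal levels can take as long as 3 months", which is naturally read as time after supplements stop, not time since a blood sample. Capsules are scheduled for 2 to 4 years after resection (12.1), including after progression (12.2), so a 6-month on-treatment value is a reasonable proxy while dosing continues. Staleness matters for participants who stop or interrupt IMP and for follow-up after treatment. With 67 months' accrual, about 7% of PFS events fall more than 3 months after the 4-year maximum, or 29–30% if everyone stopped at 2 years.
- *That the pre-operative question is also untested.* That value is in force for about a fifth to a quarter of PFS events. Under usual start-stop coding this includes progression dated at the visit 3 CT. It is pooled with the others, not absent.

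**Conclusion.** The point holds as a mismatch between sections 7.4 and 13.16 and the single model in section 19.7. One coefficient cannot separate the time points, and with no treatment interaction it cannot address response to IPE. With the baseline value in force for only about 2–6% of PFS events, the baseline question is effectively untested, while the 70–78% share for visit 3 dominates the estimate. These shares rest on exponential PFS with the protocol's medians, uniform accrual, surgery 2 to 6 weeks after randomisation, and current-value coding; I did not compute OS shares. Severity is low, because this is an exploratory endpoint at two centres.

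**What to change.** Add three models to section 19.7:
1. A Cox model from randomisation with baseline EPA as a fixed covariate. Include treatment arm and an EPA-by-treatment interaction for the question in section 13.16.
2. A Cox model with visit 2 EPA, started at a surgery landmark.
3. A Cox model with visit 3 EPA, started at a 6-month post-operative landmark, among those event-free and sampled then.

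Keep the time-dependent model as supplementary. State how EPA is valued after the last sample, which precedes the end of treatment by 18 to 42 months (24 − 6 to 48 − 6), and after IMP is stopped.

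The cost is wording and some extra analysis on samples already planned. The visit 3 landmark drops earlier events and remote participants without a visit 3 sample. An interaction estimated in a two-centre subset will be imprecise, so all three models should be reported as exploratory.

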6.5 The IMP in EMT2

Icosapent ethyl (IPE) or Vazkepa®, also known as AMR101 or Vascepa® in the USA, (Amarin Pharmaceuticals Inc.), is approved by the Medicines and Healthcare Products Regulatory Agency (MHRA), European Medicines Agency (EMA) and US Federal Drug Administration (FDA) for prevention of cardiovascular events in individuals with established cardiovascular disease, or diabetes and at least one other cardiovascular risk factor, who are already taking a statin and have elevated blood triglyceride levels at a dose of 4 g per day. It is available as 1 g (998 mg) EPA-EE in soft gelatin capsules. Therefore, each capsule contains the equivalent of 914 mg EPA-FFA. Dosing is recommended with meals. Pharmacokinetic studies have demonstrated a dose-response relationship with the plasma and red blood cell EPA level attained (and changes in other red blood cell O3FAs), with IPE 4 g/day providing a significant increase in plasma and red blood cell EPA level after 12 weeks therapy compared with 2 g/day⁴⁸. Plasma EPA levels (expressed as the % total fatty acids) in patients with hypertriglyceridaemia after 12 weeks treatment with 2 g/day and 4 g/day were 1.9% and 3.4-3.6% respectively⁴⁸⁻⁴⁹. An 8-week study in healthy volunteers of EPA FFA 2 g daily (used in EMT²⁷ and seAFOod²⁵ trials) resulted in plasma EPA levels of 4.6%⁵⁰. Treatment with EPA FFA 2 g daily for a shorter period (median 30 days) in the EMT trial (which may not have generated steady-state O3FA levels) was associated with a similar % increase in red blood cell EPA content (240%)²⁷ to that seen with IPE 2 g/day for 12 weeks (300%; cf. 500% with 4 g/day)⁴⁸. In a Japanese trial of 1800 mg EPA-EE per day for 5 years, the % change from baseline of serum EPA (as the % of total fatty acids) was only 126%⁵¹. Therefore, the available evidence suggests that dosing with 4 g/day IPE will produce EPA bioavailability most similar to that obtained with EPA-FFA and EPA-TG in previous CRC trials⁵² with the caveats that there has been no direct comparison between different EPA formulations in CRC patients and that

differences in methodology for measurement and reporting of plasma, serum and red blood cell EPA content mean that direct comparisons should be carried out cautiously.

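### The exploratory Cox model for red-cell EPA in Section 19.7 does not list treatment arm, so a real treatment effect could be reported as an effect of EPA level

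*Protocol*

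**What the plan says.** Section 19.7 measures red-cell EPA at baseline, surgery and 6 months after surgery in participants from two sites. It relates EPA content to PFS and OS by extended Cox regression, where that is suitable. The adjustment terms are the minimisation factors and regular aspirin use, the latter varying over time. For the exposure, the model "will also include red blood cell membrane EPA content as a time dependent covariate". Neither treatment arm nor an arm-by-EPA term is listed. The only extension is open-ended: "Subsequent sensitivity analyses will be conducted to adjust for any other potential effect modifiers in addition to the minimisation factors".

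Three other places bear on this:

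- Section 7.4 sets the objective: "To determine whether baseline, pre-operative and/or 6 month post-operative red blood cell EPA content predicts disease-related outcomes".
- Section 13.16 says the baseline samples "will enable the investigation of whether O3FA status predicts subsequent therapeutic response to IPE", and that levels at visits 2 and 3 "will also act as a marker of compliance to IPE".
- Section 6.5 gives the red-cell EPA increase after 12 weeks of IPE 2 g/day, with the 4 g/day figure for comparison: "300%; cf. 500% with 4 g/day".

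**The concern.** EPA is the active substance under test. Once treatment starts, a participant's EPA level depends mainly on which capsules were allocated. If arm is not in the model, the EPA coefficient takes up any effect of IPE on PFS or OS, whatever its route. The report could then say that a higher EPA level improves outcome when level makes no difference among participants on the same treatment. Such a result invites claims about target levels or dose that the data would not support.

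Separately, whether baseline status predicts response to IPE is a question about how the treatment effect varies with baseline EPA. A model without arm has no treatment effect to vary.

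**Working it through.** **1. Where arm enters Section 19.** The PFS and OS paragraphs (19.4, 19.5) and the muscle-mass and weight comparisons (19.7) all state that treatment groups are compared, so arm is implied there. The red-cell EPA paragraph has no such wording: its exposure is EPA content.

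**2. Anchor for the effect size.** Section 18.1.1 gives 247 PFS events for a hazard ratio of 0.7, 80% power and 5% two-sided. Schoenfeld's formula gives 4 × (1.960 + 0.842)² / (ln 0.7)² = 4 × 7.849 / 0.1272 ≈ 247. The figure is reproduced, and 0.7 is used below as the treatment effect.

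**3. How closely EPA level tracks arm.** Set the placebo mean to 1 and the IPE mean to 1 + rise. With 1:1 allocation and the same CV in both arms:

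- between-arm variance = rise² / 4
- within-arm variance = [CV² + (CV × (1 + rise))²] / 2
- r² = between / (between + within), and VIF = 1 / (1 − r²)

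For a 500% rise (Section 6.5) and a CV of about 10% (Section 6.2): 6.25 / (6.25 + 0.185) = 0.971, so r = 0.99 and VIF = 35. For an assumed CV of 50%: 6.25 / (6.25 + 4.625) = 0.575, so r = 0.76 and VIF = 2.4. With the 240% rise that Section 6.5 reports for the phase II trial, r runs from 0.98 (CV 10%) to 0.69 (CV 50%).

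**4. What the model would report.** In each simulated trial treatment acts at a hazard ratio of 0.7, control median PFS is 21 months, and EPA has no effect within arm. The table gives the share of trials with p<0.05 for EPA.

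| Setting | Without arm | With arm |
|---|---|---|
| Stepwise time-dependent EPA, n=128, CV 10-50%, follow-up 24-91 months | about 13-45% | 3-6% |
| One on-treatment level, n=128, CV 30-50%, censoring 24-48 months | 18-29% | 5-5.5% |
| As the row above, n=388 | 53-66% | 4.5-4.8% |

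The first row is closest to the planned analysis. The number of two-site participants is not stated; 128 is borrowed from the lean-mass calculation in Section 18.1.1. The upper follow-up of 91 months is 67 months of recruitment plus 24. The last row uses the revised minimum for the whole trial and is an upper bound only.

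**5. Mechanism check.** If about 76% of 128 participants have an event (assumed), there are about 97 events. Power of the arm comparison itself is then Φ(0.3567 × √97 / 2 − 1.96) = Φ(−0.20) ≈ 42%. The upper end of the first row is close to this, as expected if EPA is standing in for arm.

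**6. The response question.** Prediction of response needs arm, baseline EPA and their product. Section 19.7 has none of these as separate terms. If the latest value is carried forward, as is usual, the surgery sample replaces the baseline value, and Section 13.4 plans surgery within 6 weeks of randomisation. Section 19.6 does not fill the gap: its subgroups are duration of pre-operative treatment, aspirin and MSI status.

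**The case against.** **Arm is unlisted, not excluded.** A full SAP is required before analysis and is not at hand, and the sensitivity analyses are open-ended. This is fair, and the SAP may already deal with it. But the protocol names the terms of this model, so an SAP that follows it inherits the problem.

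**The objective in Section 7.4 asks only about prediction.** That stands: prediction can be computed without arm. The result could not, however, be told apart from the treatment effect, and Section 19.7 itself speaks of an effect of EPA content.

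**The simulated percentages are not false-positive rates for the Section 7.4 objective.** This also stands. They show how often a pure treatment effect would be labelled an EPA effect, and they move with the assumed sample size, CV and follow-up.

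**The link between level and arm is looser in practice.** Treatment breaks, dose reductions, over-the-counter supplements, surgery soon after randomisation and missing visit 3 samples all blur it. The 500% figure comes from another population, and Section 6.5 urges caution in such comparisons. The wide CV range and the stepwise covariate allow for some of this; the problem shrinks but remains.

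**Two stronger readings are tempting but not supported.** A reader might infer that the Section 13.16 question cannot be tested at all. It can: baseline samples are taken in both arms at the two sites, and the stated model merely lacks the term. A reader might also extend the point to the lean-mass Cox model, which "will also include lean body mass as a time dependent covariate" and likewise omits arm. Lean mass is not a near-copy of allocation, no comparable bias has been shown, and the stated aim there is only a possible association.

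**Conclusion.** The point holds for the red-cell EPA model and is minor. As written, the pooled EPA coefficient would largely reflect allocation. With a true treatment hazard ratio of 0.7 and no within-arm EPA effect, EPA would be declared significant in roughly 13-45% of trials, against about 5% with arm included. Those figures rest on an assumed 128 participants, CV of 10-50% and follow-up of 24-91 months. The direction does not depend on them; it follows from the protocol's own expectation that IPE raises EPA several-fold. Section 19.7 also omits the term needed for the response question in Section 13.16. The analysis is exploratory and limited to two sites, so the primary PFS and key secondary OS analyses are untouched.

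**What to change.** In Section 19.7:

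- **(a)** Include treatment arm in the red-cell EPA Cox model, or stratify by arm. Report the association of post-randomisation EPA with PFS and OS within the IPE arm, labelled as non-causal because illness and treatment breaks lower EPA.
- **(b)** For the Section 13.16 question, fit baseline EPA, arm and their interaction, with baseline EPA held fixed and not updated over time.

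Adding arm to the lean-mass model is optional.

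No new data are needed. The cost is precision. In the single-level simulations the standard error of the EPA term rose 1.5- to 2.2-fold once arm was added. At a CV of 10% the VIF of 35 implies about √35 ≈ 5.9-fold. An analysis within the IPE arm uses about half of an already small sample, and the interaction test will have low power with two sites. That is the information the data hold about EPA beyond allocation; the tighter interval of the pooled model is only apparent.
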